- Infection needs to be ruled out with cultures of blood, urine, and ascites (if possible), as well as
- chest X-ray and abdominal imaging if relevant. If an infection is found, antibiotics should be
- started
- If biliary obstruction is present, consultation with a gastroenterologist and/or an interventional
- radiologist should be obtained to see if the obstruction may be relieved
- A careful review of drugs, including herbal and alternative medications should be obtained

Immune-related hepatitis due to study treatment should be suspected if any of the following is seen (Immune-related hepatitis is a diagnosis made after excluding other possible etiologies for the change. Viral flare (if applicable), biliary or vascular obstruction, infection, medications, and alcohol use must be ruled out):

- AST or ALT baseline values are less than $2 \times$ ULN, and AST or ALT laboratory values increase to $\geq 5 \times$ ULN
- Among patients with baseline ALT or AST $\geq 2 \times$ ULN, levels increase to $> 3 \times$ the baseline level
- AST/ALT > 500 U/L regardless of baseline level
- Among patients with baseline Tbil levels < 1.5 mg/dL: a value of > 2.0 mg/dL
- Total bilirubin > 3.0 mg/dL regardless of baseline level management
- Interrupt study treatment and alert Bayer and Merck
- Start i.v. corticosteroid (methylprednisolone 125 mg or equivalent) followed by oral corticosteroid
- Monitor with weekly laboratory tests including AST, ALT, Tbil, Dbil, ALP, and INR.

If symptoms and laboratory tests resolve to Grade ≤ 1 or baseline (if abnormal at baseline), taper steroids over 28 days. Study treatment may be restarted after steroid treatment has been tapered to prednisone ≤ 10 mg/day (or equivalent dose of another agent).

If laboratory abnormalities do not resolve within 3 weeks, or steroids cannot be lowered to ≤ 10 mg/day (or prednisone equivalent) within 12 weeks, or patients show evidence of decompensation treatment must be permanently discontinued.

For toxicity management guidelines for pembrolizumab please refer to appendix 2, section 16.2.

Prevention/management strategies for diarrhea

Diarrhea can be a common side effect of regorafenib. The preventive/management strategies for diarrhea should be consistent with local standards (e.g., anti-diarrheals and optimized hydration status).

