7.3.1.1.3 Immune-mediated adverse reactions

Immune-mediated adverse reactions occurred in patients receiving pembrolizumab. In clinical trials, most immune-mediated adverse reactions were reversible and managed with interruptions of pembrolizumab, administration of corticosteroids and/or supportive care.

For suspected immune-mediated adverse reactions, ensure adequate evaluation to confirm etiology or exclude other causes. Based on the severity of the adverse reaction, withhold pembrolizumab and administer corticosteroids (see below). Upon improvement to Grade 1 or less, initiate corticosteroid taper and continue to taper over at least 1 month. Restart pembrolizumab if the adverse reaction remains at Grade 1 or less. If another episode of a severe adverse reaction occurs, permanently discontinue pembrolizumab.

Immune-mediated pneumonitis

Pneumonitis has been reported in patients receiving pembrolizumab. Monitor patients for signs and symptoms of pneumonitis. If pneumonitis is suspected, evaluate with radiographic imaging. Exclude other causes of pneumonitis, and manage treatment in accordance with the guidelines above. Administer corticosteroids, withhold pembrolizumab for moderate (Grade 2) pneumonitis, and permanently discontinue pembrolizumab for severe (Grade 3) or life-threatening (Grade 4) pneumonitis (see Immune-mediated adverse reactions above). If Grade 2 pneumonitis is repeated pembrolizumab will be discontinued permanently.

Immune-mediated colitis

Colitis has been reported in patients receiving PEMBROLIZUMAB. Monitor patients for signs and symptoms of colitis. Exclude other causes of colitis, and manage treatment in accordance with the guidelines above. Administer corticosteroids, withhold pembrolizumab for moderate (Grade 2) or severe (Grade 3) colitis, and permanently discontinue pembrolizumab for life-threatening (Grade 4) colitis (see Immune-mediated adverse reactions above).

Immune-mediated hepatitis

Hepatitis has been reported in patients receiving pembrolizumab. Monitor patients for changes in liver function (at the start of treatment, periodically during treatment and as indicated based on clinical evaluation) and symptoms of hepatitis. Exclude other causes of hepatitis, and manage treatment in accordance with the guidelines above. Administer corticosteroids and, based on severity of liver enzyme elevations, withhold or discontinue pembrolizumab (see Immune-mediated adverse reactions above).

Immune-mediated nephritis

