15.2 Toxicity management guidelines for immune-related AEs associated with pembrolizumab

General instructions:				

 1. Corticosteroid taper should be initiated upon AE improving to Grade 1 or less and continue to taper over at least 4 weeks. 2. For situations where pembrolizumab has been withheld, pembrolizumab can be resumed after AE has been reduced to Grade 1 or 0 and corticosteroid has been tapered. Pembrolizumab should be permanently discontinued if AE does not resolve within 12 weeks of last dose or corticosteroids cannot be reduced to ≤ 10 mg prednisone or equivalent per day within 12 weeks. 3. For severe and life-threatening irAEs, IV corticosteroid should be initiated first followed by oral steroid. Other immunosuppressive treatment should be initiated if irAEs cannot be controlled by corticosteroids. 				
Pneumonitis	Grade 2	Withhold	
 Administer corticosteroids (initial dose of 1-2 mg/kg prednisone or equivalent) followed by taper 	
 Monitor participants for signs and symptoms of pneumonitis Evaluate participants with suspected pneumonitis with radiographic imaging and initiate corticosteroid treatment Add prophylactic antibiotics for opportunistic infections
	Grade 3 or 4, or recurrent Grade 2	Permanently discontinue		
Diarrhea / Colitis	Grade 2 or 3	Withhold	
 Administer corticosteroids (initial dose of 1-2 mg/kg prednisone or equivalent) followed by taper 	
 Monitor participants for signs and symptoms of enterocolitis (ie, diarrhea, abdominal pain, blood or mucus in stool with or without fever) and of bowel perforation (ie, peritoneal signs and ileus). Participants with \geq Grade 2 diarrhea suspecting colitis should consider GI consultation and performing endoscopy to rule out colitis. Participants with diarrhea/colitis should be advised to drink liberal quantities of clear fluids. If sufficient oral fluid intake is not feasible, fluid and electrolytes should be substituted via IV infusion.
	Grade 4	Permanently discontinue		

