AST / ALT elevation or Increased bilirubin	Grade 2	Withhold	
 Administer corticosteroids (initial dose of 0.5- 1 mg/kg prednisone or equivalent) followed by taper 	
 Monitor with liver function tests (consider weekly or more frequently until liver enzyme value returned to baseline or is stable)
	Grade 3 or 4	Permanently discontinue	
 Administer corticosteroids (initial dose of 1-2 mg/kg prednisone or equivalent) followed by taper 	
Type 1 diabetes mellitus (T1DM) or Hyperglycemia	Newly onset T1DM or Grade 3 or 4 hyperglycemia associated with evidence of β -cell failure	Withhold	
 Initiate insulin replacement therapy for participants with T1DM Administer anti-hyperglycemic in participants with hyperglycemia 	
 Monitor participants for hyperglycemia or other signs and symptoms of diabetes.
Hypophysitis	Grade 2	Withhold	
 Administer corticosteroids and initiate hormonal replacements as clinically indicated. 	
 Monitor for signs and symptoms of hypophysitis (including hypopituitarism and adrenal insufficiency)
	Grade 3 or 4	Withhold or permanently discontinue ¹		
Hyperthyroidism	Grade 2	Continue	
 Treat with non-selective beta-blockers (eg, propranolol) or thionamides as appropriate 	
 Monitor for signs and symptoms of thyroid disorders.

	Grade 3 or 4	Withhold or permanently discontinue ¹		
Hypothyroidism	Grade 2-4	Continue	
Initiate thyroid replacement hormones (eg, levothyroxine or liothyronine) per standard of care	
Monitor for signs and symptoms of thyroid disorders.
Nephritis and Renal dysfunction	Grade 2	Withhold	
Administer corticosteroids (prednisone 1-2 mg/kg or equivalent) followed by taper.	
Monitor changes of renal function
	Grade 3 or 4	Permanently discontinue		
Myocarditis	Grade 1 or 2	Withhold	
Based on severity of AE administer corticosteroids	
Ensure adequate evaluation to confirm etiology and/or exclude other causes
	Grade 3 or 4	Permanently discontinue		

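### For Grade 3-4 immune-related hepatitis, Tables 6.5 and 6.6 allow pembrolizumab to restart while Appendix 15.2 stops it permanently, and nothing says which governs

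*Combined protocol and SAP*

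**What the plan says.** **Table 6.5 (Section 6.3.1).** The pembrolizumab column has five event rows. Four of them say to hold the drug and decide on restart under Table 6.6. Only the last row, AST and/or ALT above 20 x ULN, discontinues it. The table's general instructions for G3/4 rises in ALT/AST or bilirubin also send suspected immune-related hepatitis straight to Table 6.6.

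**Table 6.6 (Section 6.3.1).** Triggers for suspecting immune-related hepatitis include "AST/ALT > 500 U/L regardless of baseline level". The restart condition begins "If symptoms and laboratory tests resolve to Grade" 1 or baseline. Then: "Study treatment may be restarted after steroid treatment has been tapered to prednisone" at or below 10 mg/day. The permanent stop begins "If laboratory abnormalities do not resolve within 3 weeks"; its other two grounds are failure to taper steroids within 12 weeks and decompensation. Section 5.1.3 uses study treatment to mean both drugs.

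**Pointer.** After Table 6.6, for pembrolizumab toxicity the reader is told "please refer to appendix 2, section 16.2". The appendices are numbered 15.1 and 15.2.

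**Appendix 15.2**, titled "Toxicity management guidelines for immune-related AEs associated with pembrolizumab", has a row for "AST / ALT elevation or Increased bilirubin": withhold at Grade 2, permanently discontinue at Grade 3 or 4.

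**Section 7.3.1.1.3.** The hepatitis paragraph says "based on severity of liver enzyme elevations, withhold or discontinue pembrolizumab" and names no grades. The general irAE table withholds at Grade 3 and 4, and discontinues if steroids cannot be brought below 10 mg/day prednisone equivalent within 12 weeks. It mentions hepatitis only in its Grade 2 row, for repeated events.

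**The concern.** Two sites can each follow the protocol and treat the same patient in opposite ways. After a resolved Grade 3-4 immune-related hepatic event, a site working from Table 6.6 may give pembrolizumab again; a site working from Appendix 15.2 may not. Hepatitis is on the Section 6.2 list of pembrolizumab toxicities of interest, so the rule is likely to be consulted. At stake are re-exposure after a severe liver event and consistent handling across sites.

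A second, smaller matter lies in row 1 of Table 6.5. Its second branch, for baselines above 2 x ULN, combines a 3-fold rise from baseline with an 8 x ULN limit. The wording does not show whether that limit caps the observed value or caps the trigger.

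**Working it through.** No sample size, power or event count is involved, so the main check is to compare the rules.

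**Step 1. Apply each rule to one event.** Take suspected immune-related hepatitis with Grade 3 or 4 ALT/AST not above 20 x ULN, laboratory values back to Grade 1 within 3 weeks, steroids below 10 mg/day within 12 weeks, and no decompensation.

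| Text | Pembrolizumab |
|---|---|
| Tables 6.5 and 6.6 | Hold, then restart permitted |
| Appendix 15.2 | Permanently discontinue |
| Section 7.3.1.1.3, general irAE table | Withhold; its discontinuation condition is not met |
| Section 7.3.1.1.3, hepatitis paragraph | Withhold or discontinue by severity, no grades given |

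The same holds for a Grade 3-4 bilirubin event.

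**Step 2. Look for a reconciling rule.** None of the three permanent-stop grounds in Table 6.6 depends on peak grade. General instruction 2 of Appendix 15.2 allows resumption, but only where the drug was withheld; at Grade 3-4 the liver row discontinues it. The pointer after Table 6.6 states no precedence and gives a wrong section number.

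**Step 3. Bound the conflict.** Above 20 x ULN, Table 6.5 discontinues pembrolizumab, as the appendix does. The Grade 3-4 link comes from Table 6.5's own G3/4 instruction, so no outside CTCAE cut-offs are needed.

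**Step 4. The 8 x ULN limit in Table 6.5, row 1.** Let b be the baseline in multiples of ULN. Entry allows b up to 5 with liver metastasis and 2.5 without (Section 5.1.1).

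- *Limit as a cap on the observed value.* Branch 2 needs a peak of at least 3b and at most 8, so b can be at most 8/3 = 2.67. Above that baseline the branch can never be met. The next row for an isolated ALT/AST rise starts above 20 x ULN, because the row between needs a bilirubin rise. Table 6-1 excludes ALT/AST. Some isolated rises up to 20 x ULN then have no regorafenib dose rule.
- *Limit as a ceiling on the trigger.* Row 1 applies from the lower of 3b and 8: at b = 2.5, min(7.5, 8) = 7.5; at b = 3, min(9, 8) = 8; at b = 5, min(15, 8) = 8. Every isolated rise above 8 and up to 20 x ULN has a row at every eligible baseline.

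**The case against.** **On pembrolizumab.** Restart in Table 6.6 is permissive, whereas the appendix is mandatory, so applying the appendix satisfies both. Section 6.3.1 also refers pembrolizumab toxicity to appendix 2, and 15.2 is the second appendix, so the intended target is fairly clear. This supports letting the appendix govern. It does not remove the problem: a site following Table 6.6 exactly would do what the appendix forbids. One could argue equally that a table written for this combination overrides a general pembrolizumab guideline. The protocol says neither.

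**On Table 6.5.** A reader might infer a definite hole from 8 to 20 x ULN for isolated ALT/AST rises, above the level that Section 6.2 makes a DLT. The documents do not establish it. The trigger reading leaves no such hole, works at all eligible baselines and lines up with the 8 x ULN DLT line. Even with a cap on both branches, Table 6.6 triggers catch the whole 8-20 range at baselines up to 2 x ULN: below 2, the trigger is 5 x ULN or more; at exactly 2, it is above 3 x 2 = 6 x ULN. What remains on the trigger reading, from 5 x ULN to the lower of 3b and 8, may be a deliberate relative threshold for patients with raised baselines. The ambiguity stands, but only as a matter for clarification.

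**On row 3 of Table 6.5.** A reader might also see a conflict in leaving regorafenib unmodified at bilirubin above 2 mg/dL. That row's pembrolizumab cell already refers the event to Table 6.6, which interrupts study treatment when immune-related hepatitis is suspected. No separate point is needed.

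**Conclusion.** The contradiction on pembrolizumab is real and should be fixed. It covers suspected immune-related hepatitis with Grade 3-4 bilirubin elevation, or Grade 3-4 ALT/AST elevation not above 20 x ULN. Within those limits, the protocol both permits restart and requires permanent discontinuation, with a third rule in the general irAE table and no order of precedence. The conclusion rests on study treatment including pembrolizumab, as Section 5.1.3 states, and on the plain wording of the two tables and the appendix.

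A reader might extend this to all severe hepatic events; agreement above 20 x ULN rules that out. A reader might also infer an effect on PFS or the error rate; nothing in the documents supports one. The number of patients affected cannot be derived.

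The 8 x ULN limit in Table 6.5 is ambiguous. Whether any rise above 8 x ULN lacks a regorafenib rule depends on the reading, so no gap size is claimed.

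**What to change.** **Main change.**

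1. State in Tables 6.5 and 6.6 that Appendix 15.2 governs pembrolizumab for immune-related hepatic events, so Grade 3-4 means permanent discontinuation.
2. Begin the Table 6.6 restart sentence with: *For events not requiring discontinuation under Table 6.5 or Appendix 15.2*.
3. In the Grade 3 and 4 row of the general irAE table (Section 7.3.1.1.3), add: *hepatic events: follow Appendix 15.2*.
4. Correct the pointer from 16.2 to 15.2.

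**Clarification.** Reword branch 2 of Table 6.5, row 1, as: *ALT/AST > 2 x ULN at baseline and a rise to at least 3 x baseline or above 8 x ULN, whichever is lower*. State that row 1 applies up to 20 x ULN. The clinical leads should confirm that this is the intended meaning.

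**Cost.** Amendment wording and a letter to sites. Some patients lose the option of pembrolizumab rechallenge after a resolved Grade 3-4 immune-related hepatic event. If the sponsor wants to keep that option, the appendix must carry an explicit exception instead. Sample size and analysis are unchanged.

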6.4 Drug logistics and accountability

All study drugs will be stored at the investigational site in accordance with Good Clinical Practice (GCP) and Good Manufacturing Practices (GMP) requirements and the instructions given by the clinical supplies department of the Institution and will be inaccessible to unauthorized personnel.

6.4.1 Accountability

The investigator, or a responsible party designated by the investigator, must maintain a careful record of the inventory and disposition of the agent (investigational or free of charge) using the NCI Drug Accountability Record or another comparable drug accountability form. (See the CTEP website at <http://ctep.cancer.gov/protocolDevelopment> for the “Policy and Guidelines for Accountability and Storage of Investigational Agents” or to obtain a copy of the drug accountability form.)

6.4.2 Destruction and Return

At the end of the study, unused supplies of regorafenib and pembrolizumab should be destroyed according to institutional policies. Destruction will be documented in the Drug Accountability Record Form. The certificate of destruction should be sent to Bayer and Merck.

6.5 Treatment compliance

An adequate record of receipt, distribution, and return of all study drugs must be kept in the form of a Drug Accountability Form.

Subject compliance with the treatment and protocol includes willingness to comply with all aspects of the protocol, and to have blood collected for all safety evaluations. At the discretion of the principal investigator, a subject may be discontinued from the trial for non-compliance with follow-up visits or study drug.

6.6 Prior and concomitant therapy

All medication that is considered necessary for the subject's welfare, and which is not expected to interfere with the evaluation of the study treatment, may be given at the discretion of the investigator. All medications (including contrast media) taken within 2 weeks prior to the start of the study medication and during the study must be recorded in the subject's source documentation and in the CRF (including start/stop dates, dose frequency, route of administration, and indication). Specific caution should be taken when considering or administering a concomitant medication that is metabolized by the cytochrome enzymes CYP2C8, CYP2B6 and CYP2C9. Such concomitant medication should be avoided, if possible.

Co-administration of a strong CYP3A4 inducer (rifampin) with a single 160 mg dose of regorafenib decreased the mean exposure of regorafenib, increased the mean exposure of the active metabolite M-5, and resulted in no change in the mean exposure of the active metabolite M-2. Avoid concomitant use of regorafenib with strong CYP3A4 inducers (e.g. rifampin, phenytoin, carbamazepine, phenobarbital, and St. John's Wort)

Co administration of a strong CYP3A4 inhibitor (ketoconazole) with a single 160mg dose of regorafenib increased the mean exposure of regorafenib and decreased the mean exposure of the active metabolites M-2 and M-5. Avoid concomitant use of regorafenib with strong inhibitors of CYP3A4 activity (e.g. clarithromycin, grapefruit juice, itraconazole, ketoconazole, nefazadone, posaconazole, telithromycin, and voriconazole).

Permitted concomitant therapy includes:

- Standard therapies for concurrent medical conditions.
- Supportive care for any underlying illness.
- Palliative radiation therapy is allowed if the target lesion(s) are not included within the radiation field and no more than 10% of the bone marrow is irradiated.
- Granulocyte colony-stimulating factor (G-CSF) and other hematopoietic growth factors may be used in the management of acute toxicity, such as febrile neutropenia, when clinically indicated or at the investigator's discretion. However, they may not be substituted for a required dose reduction. Subjects are permitted to take chronic erythropoietin.
- Treatment with nonconventional therapies (such as acupuncture), and vitamin/mineral supplements are permitted provided that they do not interfere with the study endpoints, in the opinion of the investigator.
- Bisphosphonates

- Subjects who are therapeutically treated with an agent such as warfarin or heparin will be allowed to participate provided that their medication dose and INR/PTT are stable. Close monitoring (day 5 of cycle 1 and day 1 of each cycle) is mandatory. If either of these values are above the therapeutic range, the doses should be modified and the assessments should be repeated weekly until they are stable.

The following are not permitted:

- Other investigational treatment during or within 2 weeks before starting study treatment
- Systemic antitumor therapy, including cytotoxic therapy, signal transduction inhibitors, immunotherapy, and hormonal therapy
- Bone marrow transplant or stem cell rescue
- Subjects taking narrow therapeutic index medications should be monitored proactively (e.g. warfarin, phenytoin, quinidine, carbamazepine, Phenobarbital, cyclosporin, and digoxin). Warfarin is metabolized by the cytochrome enzyme CYP2C9 and its levels may be especially affected by regorafenib
- Use of any herbal remedy (e.g. St. John's wort [*Hypericum perforatum*])
- Please note: Patients should be seen frequently / early during treatment as per Prescribing Information
- Liver function tests should be obtained before initiation of regorafenib and monitored at least every 2 weeks during first 2 months of treatment. Thereafter liver function should be monitored monthly or more frequently as clinically indicated
- Monitor blood pressure weekly for the first 6 weeks of treatment and every cycle or more frequently as clinically indicated.

7. Timing of assessments

Potential candidates will undergo screening as outlined in calendar, **study treatment has to be started within 7 days of screening.**

All subjects will be seen weekly for the first two cycles and every 3 weeks afterwards (coordinated with days of pembrolizumab administration). Tumor measurement should be done every 8 weeks.

Each cycle can be started within 5 days of expected dates to accommodate for scheduling issues.

	Screening	Cycle 1 and 2			Cycle 3 on			Follow-up	
		Day 1	Day 8	Day 15	Day 1	Day 8	Day 15	End of TX 30 days (+/- 7 days) of last tx date	FU phone call every 6 months (+/- 7 days) for 24 months
Informed consent, Review of Eligibility Criteria	X ²								
Medical History & Demographics	X ²								
Physical Exam (including vital signs), Weight, Performance Status	X ²	X	X	X	X			X	
Tumor biopsy (optional and encouraged)				X*					
PT/INR, PTT, aPTT	X ²		X	X*					
Serum pregnancy test ³	X ¹	X			X				
CBC, CMP (Safety and follow up)	X ¹	X	X	X	X				
Lipase	X ²								
Urinalysis (Safety)	X ¹								
ECG (Safety)	X ²								
TSH, Free T4 (Safety and f/u)	X ²	X			X			X	
Radiology scans for tumor measurement	X ²						X**	X**, ⁶	
Blood sample for SNP			X ⁴						
Blood sample for DNA/RNA and PBMC***	X ⁵				X ⁵			X ⁵	
Archival Tumor Tissue (paraffin embedded) Minimum 10 slides @ 5 micron thickness unstained/unprocessed	X								

Pill diary and compliance		X			X			X	
Toxicity Assessment/AE (CTCAE V5)		X	X	X	X			X	
Regorafenib		X	X		X	X			
Pembrolizumab		X			X				
Concomitant meds		X			X				
End of study/start of new treatment								X	X

* biopsy can be done between day # 11 and day # 19 of cycle 1 only, PT/INR, PTT to be done within one week of biopsy

** Seven day window, CT scan is preferred to other modalities unless there are contraindications to the scan and contrast

*** Collection only at baseline, C3D1 and EOT

1 within 7 days of Cycle 1 Day 1

2 within 28 days of Cycle 1 Day 1

3 for women of child bearing potential only

4 purple top. Send specimen to [name] lab.

5 Two speckled top, one gold top as well as four yellow top tubes. The yellow tubes will go to USC Norris Cancer Center IMC Lab ([name]) and speckled top and gold top to Pathology lab, [name]

6 If last imaging within 3 weeks of this date, no need to repeat scans.

All screening procedures done within 72 hours of C1D1 do not need to be repeated

If the timing of a protocol-mandated study visit coincides with a holiday and/or weekend that precludes the visit, the visit should be scheduled on the nearest following feasible date, with subsequent visits rescheduled accordingly. A +/- 3 day window is allowed for scheduling of study visits that must be moved for other reasons

Contact information:

[name] [name]
 USC Norris Cancer Center IMC Lab
 [name]
 [name]
 [contact]
 Contact: [contact]
 Office: [contact]
 [contact]

[name]
 USC Clinical Laboratories, [name]
 [name]
 [name]
 [contact]
[contact]

[name] laboratory
 USC Norris Cancer Center
 [name]
 [name]
 [name]
 [contact]
 Attn: [name]

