6.1 Treatments to be administered

Drug	Dose/Potency	Dose Frequency	Route of Administration
Pembrolizumab	200mg	Q3weeks	IV
Regorafenib	Per dose schedule (phase I) RD (Phase II)	Daily days 1-14 of 21 day cycles	PO

Regorafenib starting dose, dose level 1	80mg	Days 1-14
Regorafenib dose level 2	120mg	Days 1-14

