6.2 Treatment assignment

This is an open label phase I/II trial. Patients will receive regorafenib at escalating doses or RD for 14 days and pembrolizumab q3weeks.

All patients (phase I and II) will be seen on a weekly basis for the first 8 weeks for toxicity checks using CTCAE and will have response assessment with CT scan every 8 weeks.

Rules for dose escalation, dose expansion, and termination of escalation are given below.

Dose Limiting Toxicity (DLT)

As a general rule, DLT includes the observation of any of the side effects listed below during the DLT evaluation period and will ultimately be determined upon deliberation between subsites and the principal investigator of the trial. The principal investigator and the study team will have weekly safety meetings and conference calls during phase I period. Monthly meetings will be held monthly for the first 20 patients on phase II and if no unexpected signal of toxicity is observed the frequency of the meetings will be annual to correspond with the reporting period to Data and Safety Monitoring Committee at USC (DSMC). Furthermore, the opinion of the DSMC at USC can be sought as required on an ad hoc basis.

- Hematotoxicity:

- Persistent grade 4 neutropenia lasting ≥ 7 days;

- neutrophil count of $< 1000/\text{mm}^3$ with a single temperature of $> 38.3^\circ\text{C}$ or a sustained temperature of $\geq 38.0^\circ\text{C}$ for more than one hour.

- Grade 4 thrombopenia or thrombopenia associated with a hemorrhage requiring platelet transfusion.

- Grade 3 thrombocytopenia with bleeding.

- Grade 4 anemia.

- Non-hematotoxicity, please see separate liver and non-liver related information below.

- Liver related toxicities

- ALT/AST increases 5-8 X ULN with concomitant bilirubin increase $< 2 \times$

- ULN not resolving to $< 5 \times$ ULN within 7 days
 - ALT/AST increases $5-8 \times$ ULN with concomitant bilirubin increase $> 2 \times$ ULN
 - ALT/AST increases $> 8 \times$ ULN regardless of concomitant bilirubin increase
 - Bilirubin increase $> 3 \times$ ULN not resolving to baseline within 7 days
- Grade ≥ 3 non-liver related with the following specifications:
 - \geq Grade 3 diarrhea, nausea, vomiting, and loss of appetite for ≥ 5 consecutive days (despite supportive therapy);
 - \geq Grade 3 fatigue for ≥ 7 consecutive days;
 - \geq Grade 3 electrolyte imbalance for ≥ 7 consecutive days (despite supportive therapy);

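### The 8-week scan rule and the calendar's Cycle 3 Day 15 scan mark agree only on the first scan, and nothing says whether scans stay on calendar dates when a cycle is delayed

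*Combined protocol and SAP*

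**What the plan says.** Section 6.2 says that all patients "will have response assessment with CT scan every 8 weeks". Section 7 repeats the interval: "Tumor measurement should be done every 8 weeks". Neither states a starting point for the count.

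In the Section 7 calendar, the row "Radiology scans for tumor measurement" is marked at screening, under Day 15 of the column group headed Cycle 3 on, and at end of treatment. The footnote on the last two marks begins "Seven day window, CT scan is preferred to other modalities". It gives no interval and no reference date.

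Section 6.1 sets the cycle length: "Daily days 1-14 of 21 day cycles". Section 7 ties visits after cycle 2 to pembrolizumab days and adds "Each cycle can be started within 5 days of expected dates to accommodate for scheduling issues". For holidays and weekends, "the visit should be scheduled on the nearest following feasible date, with subsequent visits rescheduled accordingly". Table 6-1 allows a regorafenib delay of 4 weeks, or longer with clinical benefit. The skin-toxicity guidance in Section 6.3.1 and Appendix 15.2 let pembrolizumab be held and resumed within 12 weeks of the last dose.

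PFS is the phase II primary endpoint. Section 10.1 compares it with a historical median of 1.9 months and gives a critical value of 2.44 months.

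**The concern.** Eight weeks is not a whole number of 21-day cycles, so an 8-week rule cannot be carried by a fixed day of the cycle. A site working from the text and a site working from the calendar would schedule the second and later scans differently.

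The second difficulty is the anchor. A mark on a cycle day moves when the cycle moves. Radiographic progression is dated at the scan that shows it. If the first scan comes later in patients whose cycles were delayed for toxicity, their recorded PFS can lengthen without any change in the tumour's course. There is no concurrent arm scanned on the same clock to absorb this, and Section 3 foresees one or two further sites.

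**Working it through.** **Inputs.** Cycle length 21 days (6.1); interval 8 weeks (6.2, 7); scan mark on Day 15 from cycle 3 (calendar); n = 63, medians 1.9 and 2.85 months, one-sided alpha 0.1, power 80%, critical value 2.44 months (10.1). One month is taken as 30.4375 days.

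**The plan's own figures.** Under exponential PFS, test S at 1.9 months: S0 = 0.50 and S1 = 0.5^(1.9/2.85) = 0.630. On the log(−log S) scale, v(S) = (1 − S)/(S·ln²S), so v(S0) = 2.081 and v(S1) = 2.751.
- n = (1.2816·√2.081 + 0.8416·√2.751)² / (ln 1.5)² = 64.04, or 65 rounded up, against 63 stated. Power at 63 is 0.795.
- Critical value with the average variance: 1.9·exp(1.2816·√(2.416/63)) = 2.44 months, as stated.

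The design figures therefore reproduce closely. This point does not touch them.

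**Scan dates without delays.** C3D15 is day 2×21 + 15 = 57, that is, 56 days or 1.84 months after C1D1.

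| Reading | Second scan | Third scan |
|---|---|---|
| 8-week text | day 113 = C6D8 (3.68 months) | day 169 = C9D1 (5.52 months) |
| Day 15 of every cycle from 3 (literal) | day 78 = C4D15 (2.53 months) | day 99 = C5D15 (3.22 months) |
| C3D15 only | none shown | none shown |

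No reading of the mark yields the 8-week series after the first scan.

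**Effect of the reading, without delays.** Assume exponential progression, recorded at the next scan, with no events dated between scans. In 20,000 simulated trials of 63 patients:

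| True median | Reading | Typical observed median | P(observed median > 2.44) |
|---|---|---|---|
| 1.9 | 8-week text | 3.68 | 0.56 |
| 1.9 | literal calendar | 2.53 | 0.57 |
| 2.85 | 8-week text | 3.68 | 0.99 |
| 2.85 | literal calendar | 3.22 | 0.99 |

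The probabilities match because neither schedule has a scan between 1.84 and 2.44 months. The reported estimates do differ. Three months is day 91, so recorded 3-month PFS equals S at the last scan before it: S(56 days) under the text and S(77 days) under the literal calendar. That is 0.51 versus 0.40 at a true median of 1.9 months, and 0.64 versus 0.54 at 2.85.

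**Effect of the anchor.** With scans tied to C3D15, a 4-week cycle delay moves the first scan from week 8 (1.84 months) to week 12 (12×7/30.4375 = 2.76 months). The critical value falls at week 10.6.

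The share of patients delayed, p, is not in the documents, so a range is shown. If the delay takes the first scan past week 10.6, the share recorded as progressed by 2.44 months is (1 − p)·(1 − S(56 days)). At a true median of 1.9 months, S(56 days) = 0.511. The observed median of 63 exceeds 2.44 when at most 31 patients are recorded by then (binomial).

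| p (assumed) | Recorded by 2.44 months | P(observed median > 2.44) |
|---|---|---|
| 0 | 0.489 | 0.57 |
| 0.1 | 0.440 | 0.83 |
| 0.2 | 0.391 | 0.96 |
| 0.3 | 0.342 | 0.99 |

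Shorter delays need not act the same way. A 2-week delay puts the scan at week 10 (2.30 months), still below 2.44. With p = 0.2 the probability is then 0.47, slightly lower than with no delay.

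**The case against.** **The text governs, and C3D15 is week 8.** Two sentences give the interval in weeks, and the mark falls exactly on the first 8-weekly date. A first scan at C3D15 and every 8 weeks after that is a plausible intention. A reader might infer from the column heading a rule of scanning every 3 weeks. The documents do not support that as a rule: no section states it, and marks in that column group are not uniformly per cycle, since the blood-sample row carries the note "Collection only at baseline, C3D1 and EOT". What stands against the plan is that the scan row has no comparable note, so the calendar does not state the 8-week interval either.

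**Sites would not drift.** A week-12 scan departs from the 8-week sentences. The rescheduling clause concerns holidays and weekends, not dose holds. A hold of regorafenib alone need not move a visit coordinated with pembrolizumab. All of this is correct, and it limits the slip to delays of whole cycles at sites that follow the cycle-day mark. But the seven-day window is attached to that mark, and nothing says that the 8 weeks run from C1D1 regardless of delay.

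**The size is fragile.** This also stands. At a true median of 1.9 months, S is 0.511 at 56 days and 0.499 at 58 days, so the 3.68 versus 2.53 contrast rests on a knife-edge inside the scan window. Section 7.2 counts clinical progression, and deaths also count. If 20% of events are dated between scans (assumed), the probability of exceeding 2.44 months falls to about 0.44 under both readings. If the historical 1.9 months already reflects scan timing, the inflation is smaller again.

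**Conclusion.** The text and the calendar do not match after the first scan, and the anchor is undefined. Both follow from the documents without any assumption.

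Without delays, the consequence is limited to the dating of later progressions and to reported estimates, such as 3-month PFS. A reader might take the gap between medians, up to 1.15 months, as evidence that the choice of reading could decide the trial. The calculation does not bear that out: the chance of passing 2.44 months is 0.56 or 0.57. Compared with the 8-week text, the literal calendar dates later progressions earlier, not later.

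The anchor matters more. A 4-week cycle delay would carry a C3D15 scan from 1.84 to 2.76 months, across the critical value. How far this could move the result depends on three unknowns: the share of patients with whole-cycle delays long enough to pass week 10.6, whether sites follow the cycle day, and how many events are dated between scans. The delay probabilities above are illustrations under exponential PFS with a latent median of 1.9 months. They are not estimates of the trial's error rate, and a bias of known size cannot be claimed. The sample size is unaffected.

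Section 9 shows a related mismatch: it places a liquid biopsy at the first restaging, while the calendar collects that blood at C3D1, day 43.

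**What to change.** Replace the Day 15 mark with a separate calendar line: tumour assessment at day 57 (±7 days) and every 56 days (±7 days) thereafter, counted from C1D1 by calendar date and not moved for dose holds, cycle delays or rescheduled visits. Use the same sentence in Sections 6.2 and 7.

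The cost is one calendar line and one sentence. Some scans will fall in weeks without a clinic visit. No scans are added compared with the 8-week rule already in the text.
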